Our long-term goal is to develop a biomarker of treatment in patients receiving ECT. By having this biomarker, practitioners could move towards individualized treatment parameters. We hypothesize that ictal power and post-ictal infra-slow waves will be associated with clinical response and the choice of anesthetic agent will accentuate ictal or post-ictal morphology. We propose a pilot project using dcEEG to look at infra-slow waves in depressed patients receiving ECT randomized to ketamine or methohexitol. The rationale for this project is to identify biomarkers of treatment adequacy in ECT, which could lead to decreased morbidity and mortality with the procedure and lessen the burden of depression in our patient population.

Aim 1: Identify EEG biomarkers related to clinical response

PROTOCOL TITLE:

Hypothesis 1.1: Ketamine will be associated with increased ictal power and increased post-ictal suppression compared to methohexital

Hypothesis 1.2: Methohexital will be associated with post-ictal infra-slow waves

Hypothesis 1.3: Increased ictal power and infra-slow waves will be associated with clinical outcomes

At the completion of this pilot project, we expect to identify infra-slow characteristics using dcEEG that correspond with clinically effective treatment. We plan to further evaluate these phenomena as a potential biomarker of treatment adequacy with the goal of individualizing ECT treatments and improving standard of care.

2. Background

[figure not shown]
Historically it was thought that inducing a seizure was all that was needed to produce the clinical effects seen in ECT, but multiple studies across the past 8 decades have shown varying rates of efficacy and severity of side effects based on ECT stimulus parameters. We learned empirically that electrode placement (bitemporal versus unilateral) and stimulus parameters that affect electrical pulse and pulse train matter [10]. However, practitioners continue to focus on total charge as the primary metric, largely ignoring the role individual stimulus parameters play in the equation.

A biomarker of treatment response would help in evaluating clinical efficacy and accelerate evaluation of individual ECT parameters. There have been many potential biomarker for depression including hormones, cytokines, and neuro-imaging. These investigations have

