Neuropsychological Assessments: The Montreal Cognitive Assessment, a measure of global cognitive function that is sensitive to gross neurocognitive abnormalities, will be used for screening for preexisting cognitive impairment [20, 21]. The Dot Counting Test will measure effort. The Test of Premorbid Function estimates premorbid intellectual function [22] that will be used as a potential covariate in analyses. The Autobiographical Memory Test will assess free recall and retrieval patterns (specific versus general) of retrospective autobiographical memories [23-25]. The Hopkins Verbal Learning Test-Revised (HVLT-R) will measure learning strategies, free recall, and recognition memory [26]. The Delis Kaplan Executive Function System (DKEFS) Color-Word Interference and Verbal Fluency Test measures processing speed, sequencing and cognitive flexibility [27-31]. To minimize practice effects, we will use three different published versions of the HVLT-R at each time point [32]. Also, we will construct a reliable change index for all cognitive variables of interest [33]. Following published guidelines, we will compute the HVLT-R percent retention score, which will be our primary outcome measure [34]. The percent retention score is a useful measure of hippocampal dependent memory function that reduces the possibility of over-estimating memory function from immediate and delayed free recall scores [34]. The entire neuropsychological battery (completion time < 60 minutes) will be used to compute composite z-scores that represent global cognitive function at each time point for secondary analysis.

ECT: The treating anesthesiologist will determine the appropriate dose for this procedure. The anesthetic agents include methohexitol and ketamine, general anesthetics, and succinylcholine, a depolarizing neuromuscular blocker. Subjects will be randomized into methohexitol and ketamine arms prior to the first ECT treatment. Both induction agents are considered standard of care during ECT. The first ECT session will determine individual seizure thresholds to ensure subsequent treatments are delivered at supra-threshold intensities. Motor, electroencephalographic and heart rate parameters will be recorded for each treatment.

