Study Protocol: Subjects will receive their baseline depression and cognitive assessment 0 to 48 hours prior to the first ECT session (T1). One day after the sixth ECT treatment (T3), subjects will receive their second depression and cognitive assessment. Treatments will continue thrice weekly until clinical response, which

PROTOCOL TITLE:

typically occurs between six and twelve treatments. The final assessment will occur after their last ECT treatment in the series (T4) and will include depression and cognitive assessments. DcEEG data will be collected at T1-T4 using a non-invasive cap that covers the patient's head. Per standard of care, change of electrode placement will be assessed at the midpoint (T2) by the treating psychiatrist. If the patient is not responding to ECT they may be switched from RUL to bitemporal placement. This assessment will not be affected by the research protocol.

13. Data Analysis

See effect size calculation in question #5 for hypothesis 1.1. To the best of our knowledge, spreading depression has never been studied in ECT (aside from our preliminary findings). We will use the effect size for hypothesis 1.1 to guide us. In terms of analyzing the mean power of the waves noted, we plan to calculate the sum of the mean power per epoch across T1-T4 data points to get total ictal power, as well as smaller epochs to calculate total infra-wave power and post-infra-wave suppression. We will also use chisq to compare number of infra-slow waves and t-tests to compare power of infra-slow waves and total ictal power of seizures and post-ictal suppression in the methohexitol group. We do not expect to see infra-slow waves in the ketamine group.

14. Provisions to Monitor the Data to Ensure the Safety of Subjects

Methohexitol and ketamine are both standard of care anesthetic agents used in ECT and the dcEEG device is worn on the scalp and is non-invasive. If the patient does not tolerate the anesthetic chosen, then they will be switched to the other anesthetic and act as a cross-over cohort. The medications and ECT device used in this study are standard of care. In the unlikely event that at the midpoint assessment (6 months) greater than 50% of patients have refused to wear the EEG cap, our study will not be sufficiently powered and will be terminated.

15. Withdrawal of Subjects

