locked cabinets and in password-protected databases, separate from any clinical data. These will only be accessible by key study personnel. A link between study code numbers and direct identifiers will be retained in order to contact subjects for visit appointments or at a later date to inform them of newly received information. This link will be retained for the duration of the study. Subjects will be identified only by unique Patient ID numbers in Case Report Forms (CRFs) and electronic CRFs. The CRFs will be maintained in a locked cabinet housed in the Center for Psychiatric Research. These documents will only be accessible by authorized study staff and will comply with HIPPA requirements for the storage of health information. Moreover, all information will be in double-locked rooms per HIPAA specifications. At the time of study closure, all participant identifiers (name, address, etc.) will be made inaccessible to the research team. The results of this research may be presented at meetings or in publications; however, participants' identity will not be disclosed. The participant will be provided with a copy of the consent form to take home upon request.

Devices:

MECTA Spectrum 5000Q (Electroconvulsive Therapy): The UNM ECT service has two MECTA 5000Q ECT machines for inpatient and outpatient ECT services.

Stimulus output

- Current: 800 mA constant current, limited to 450volts
- Frequency: 10 to 120 Hz, in 10 Hz increments
- Pulse width: 0.3 to 1.0 ms, in 0.25 ms increments
- Duration: 0.50 to 8.0 s
- Maximum output: standard maximum output 576 mC Recording Channels
- Channels 1 & 2, EEG Stimulus Generation
- Waveform
- Bipolar
- Brief pulse
- Square wave

dcEEG: The 24-channel EEG monitoring (<https://mbraintrain.com/smarting/>) will include the low frequency range (< 0.01). EEG set-up will be facilitated with the use of a skull cap that includes the multi-channel electrodes. The EEG signal will be digitally recorded for approximately 30-minutes (pre- and post-ECT) and transferred to a dedicated device over Bluetooth. This dedicated device will not be on the network.

17. Data and Specimen Banking

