Participation in this study may involve minimal risk and/or discomforts associated with repeated cognitive testing and the time taken to place the dcEEG cap on their head prior to treatment at four different time points (T1-T4). The anesthetic agents are both standard of care in ECT. There is a risk of side effects with these medications, but these risks are no higher than if they were not in the study.

19. Potential Benefits to Subjects

There is no anticipated benefit for subjects.

20. Recruitment Methods

The UNM ECT Treatment Program receives referrals from inpatient and outpatient providers at the UNM Mental Health Center. The treatment team will clinically determine who will be eligible for the study and document this in the subject's study records. The research team will only approach patients for the study protocol that have been identified by the primary treatment team. Patients diagnosed with Major Depressive Disorder and Bipolar Disorder currently Depressed are eligible for ECT treatment will be recruited from the UNM ECT Treatment Program.

21. Provisions to Protect the Privacy Interests of Subjects

From the standpoint of privacy and confidentiality, the subject's welfare will be safeguarded by responsible, systematically controlled procedures in the collection of information for both clinical and research purposes. Subjects may refuse to answer any question at any time. Recorded information for research purposes will be identified only by subject initials and a study code number. Subject data will be kept in locked cabinets in the research clinic with limited access granted only to designated research personnel. These processes will be in place throughout the entire research process, from initial consenting to research, through research procedures, and follow-up. The study PI will maintain confidentiality of all records to the extent permitted by applicable laws.

22. Economic Burden to Subjects

Subjects will be not placed under economic burden due to this trial.

23. Compensation

This study will require data gathering at 4 points (T1-T4). Subjects will be compensated \$50.00 for completion of wearing the dcEEG cap. They will receive \$50.00 for participating in the cognitive and depression assessments for each visit (up to 3 visits). The most compensation a patient can receive is \$200.00. The compensation is for the

PROTOCOL TITLE:

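### Section 13 gives the planned pre-ECT dcEEG no role and post-ictal suppression no reference level, leaving precision unused and one outcome undefined

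*Combined protocol and SAP*

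**What the plan says.** - **Recording.** Section 16 (Devices, dcEEG): "The EEG signal will be digitally recorded for approximately 30-minutes (pre- and post-ECT". Section 12 limits this to four study points: "DcEEG data will be collected at T1-T4 using a non-invasive cap". Section 18 confirms that the cap goes on beforehand, mentioning "the time taken to place the dcEEG cap on their head prior to treatment at four different time points (T1-T4". No section says whether the pre-ECT part begins before or after anaesthetic induction.
- **Derived measure.** Section 13: "we plan to calculate the sum of the mean power per epoch across T1-T4 data points to get total ictal power". Infra-slow power and suppression come from shorter epochs. No ratio, normalisation or EEG covariate is named, and suppression has no formula.
- **Tests.** Section 13 uses chi-square for the number of infra-slow waves and "t-tests to compare power of infra-slow waves and total ictal power of seizures and post-ictal suppression in the methohexitol group". The clause ends on one arm only. The between-arm test has to be read from hypothesis 1.1 in Section 1: "Ketamine will be associated with increased ictal power and increased post-ictal suppression compared to methohexital". Section 13 names no model for hypothesis 1.3, which relates power to clinical outcome.
- **Covariates.** The only one named is the premorbid function test in Section 12, which "estimates premorbid intellectual function [22] that will be used as a potential covariate in analyses".

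**The concern.** Three things are at stake.

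1. **Precision.** Power measured at the scalp is likely to differ between patients for reasons unrelated to the seizure. That is general reasoning; the documents neither state nor quantify it. To the extent that it is true, an unadjusted t-test carries this variation as noise, and 11 per arm leaves little room for noise. The pre-ECT segment is the natural measure of it.
2. **Meaning.** Suppression is a reduction from some level. Without that level, the second half of hypothesis 1.1 cannot be computed from the plan. This holds whatever the correlation between pre-ECT and later power.
3. **Hypothesis 1.3.** Power is not assigned at random. If a patient's background amplitude is also related to clinical response, an association between power and outcome could reflect amplitude and not the seizure.

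**Working it through.** **Inputs from Section 5:** d = 1.19, two-sided alpha 0.05, power 0.80, 11 per group, 15% attrition, 26 recruited. **Assumed:** the correlation r between pre-ECT log power and the outcome, shown over a range; and that d = 1.19 applies on the log scale.

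**1. The plan's own figure.**
- Normal approximation: n per arm = 2 × ((1.960 + 0.842)/1.19)² = 11.09, which rounds up to 12. Power at 11 per arm is 79.7%.
- Exact two-sample t-test: n = 12.12, so 13 per arm. Power at 11 per arm is 75.6%.
- Attrition: 22/(1 − 0.15) = 25.9, so 26.

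The stated 11 and 26 reproduce to within two patients per arm. The sample size does not depend on this point.

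**2. Adjusting for one baseline covariate.** The residual SD shrinks by √(1 − r²), so the effective standardised difference is d/√(1 − r²). With n = 11 per arm the non-centrality is that value × √(11/2), on 2n − 3 = 19 degrees of freedom.

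| r (assumed) | d/√(1 − r²) | Power, 11 per arm | d detectable at 80% power | n per arm for 80% power |
|---|---|---|---|---|
| 0 | 1.19 | 75.4% | 1.26 | 13 |
| 0.3 | 1.25 | 79.2% | 1.20 | 12 |
| 0.5 | 1.37 | 86.3% | 1.09 | 10 |
| 0.7 | 1.67 | 95.9% | 0.90 | 7 |

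The unadjusted comparator is 75.6%. At r = 0 the spent degree of freedom costs 0.2 percentage points.

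**3. A simple change score (a log ratio with no covariate).** If pre-ECT power and outcome have equal variance, the variance is multiplied by 2(1 − r). Power at 11 per arm is then 47%, 61%, 76% and 93% at r = 0, 0.3, 0.5 and 0.7. It gains on the unadjusted test only if r exceeds 0.5. A ratio is therefore justified by giving suppression a meaning, not by precision, and the covariate should stay in the model beside it.

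**4. Chance imbalance.** The difference between arms in mean baseline amplitude has SD √(2/11) = 0.43 patient-SDs. It exceeds 0.5 SD with probability 2 × (1 − Φ(0.5/0.43)), about 24%. An imbalance of 0.5 SD at r = 0.5 would shift the unadjusted difference by 0.5 × 0.5 = 0.25 outcome SDs, about a fifth of the planned 1.19.

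**The case against.** **Silence is not exclusion.** A reader might infer that the pre-ECT recording will go unused and that every marker is an absolute power. The documents do not say so. They never use the word absolute, they do not rule out normalisation, suppression has no stated formula, and the number of infra-slow waves is not a power measure at all. What stands is that no role, normalisation or reference level is specified.

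**Randomisation.** A reader might also infer that differences in patients' amplitude bias the arm comparison. They do not: they balance in expectation, and covariate adjustment is optional in a randomised comparison. For hypothesis 1.1 the loss is precision. The objection does not reach hypothesis 1.3.

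**The anaesthetic's own effect on the EEG.** A third tempting reading is that baseline adjustment would separate the seizure from the drug's background effect. It would not. A covariate or ratio based on a pre-induction segment leaves that effect in full. A post-induction, pre-stimulus segment could address it, but it is itself affected by arm and so answers a different question. Section 1 hypothesises that the choice of agent accentuates ictal or post-ictal morphology, so the agent's total effect may be the contrast the sponsor wants.

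**Size.** At r = 0.3 the gain is under four percentage points, and this is a pilot. The planning effect compares threshold with suprathreshold groups, not these two agents. Both points are fair. They limit the precision argument but not the missing definition of suppression.

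**Infra-slow power.** Section 13 expects no infra-slow waves under ketamine, so an adjusted arm comparison of that measure would have little content. The change below is limited to ictal power and suppression.

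**Conclusion.** The point holds as an omission in Section 13. A pre-ECT dcEEG is planned at T1 to T4, the analysis specifies no role for it, and post-ictal suppression has no reference level. For hypothesis 1.1 the consequence is lost precision and exposure to chance imbalance. For hypothesis 1.3 it is possible confounding, conditional on amplitude being related to clinical response, which the documents do not address.

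At 11 per arm and d = 1.19, power moves from about 76% to between 75% and 96% across r = 0 to 0.7. This rests on the assumed r and on d = 1.19 carrying over to log power and to this contrast of agents. The need to define suppression rests on neither. The trial can run without the change, but the suppression result would be hard to interpret.

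**What to change.** In Section 13:

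1. State when the pre-ECT recording starts, and start it before induction at T1 so that the covariate precedes any study anaesthetic.
2. Replace the t-tests of ictal power and post-ictal suppression between arms with a linear model of log power on arm, adjusted for T1 pre-ECT log power in the same leads and frequency band.
3. Define post-ictal suppression as the log ratio of post-ictal to same-session pre-ECT power, and keep the T1 covariate in its model. From T2 onward the same-session reference is recorded after randomisation, so report the result as a within-session change.
4. Include the same T1 covariate in the models for hypothesis 1.3.
5. If a post-induction, pre-stimulus segment is available, use it only as the reference in a sensitivity analysis, labelled as estimating the effect beyond the agent's background effect.

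Fix this wording before data are seen, because choosing a reference afterwards with 22 patients invites selection.

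**Cost:** analysis wording, a little more signal processing and one degree of freedom, with a trivial loss of power if the correlation is near zero. No new visit is needed. If the T1 recording would otherwise have begun after induction, it has to start earlier.
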